# 7.2 Handling of Dropouts, Missing Data

The analyses will be done without adjustments for missing values. Subjects who withdraw or are lost to follow up will be censored at the last time of surveillance. Primary analysis will be analyzed on the mITT population and any missing swabs will be considered missing completely at random. A sensitivity analysis will repeat the primary efficacy analysis on the PP population.

# 7.3 Multiple Comparisons and Multiplicity

Primary efficacy and relative efficacy are assessed by only one endpoint and will not be adjusted for multiplicity.

# 7.4 Subgroups

Subgroup analysis will be performed with the subgroup as a categorical variable and tested for interaction with vaccination.

The efficacy analyses will be performed for the following subgroups as feasible:

Time since last immune challenge (prior vaccine or infection) as a category of >1 year, 6 months-1 year, 3 to 6 months and age category (18-49 and 50+)

#### 7.5 Derived and Computed Variables

#### **Demographics**

Age, if not already provided, will be calculated in years using the following formula: Age (years) = (Date of Visit 1 - Date of Birth + 1) / 365.25, round to smallest integer

Body Mass Index (BMI, kg/m^2) will be calculated using the following formula:

$$BMI = Weight (kg) / Height2 (m^2)$$

# **Efficacy**

#### Time at Risk

- Beginning of time at risk starts with the first active surveillance contact
- End of time at risk is illness onset with rapid test confirmed SARS-Co-v2 virus infection or the last submitted response to study surveillance.
  - o Illness onset is defined for participants with an illness as the earlier of the first positive swab collection (excluding false positives) and the date of reported symptom start.
- Duration of time at risk in days is defined as: End of time at risk beginning of time at risk + 1.
- We will assess the need to statistically adjust for time since last infection or time since last vaccination as 2 separate potential covariates

#### 7.6 Analysis Software

All analyses will be performed using SAS® Software version 9.4 or higher or R version 4.1.2 or higher.

#### 7.7 Data Transformation

None

#### 8. STATISTICAL ANALYSIS

#### 8.1 General Principles

Superiority confidence intervals (CIs) will be two-sided with a 95% confidence level, and superiority hypothesis tests will be evaluated at two-sided significance level of 0.05. Non-inferiority hypothesis tests will be evaluated with a one-sided 95% confidence interval. Descriptive summaries for interval scale variables will include number of participants with evaluable information, mean and standard errors. Descriptive summaries for categorical scale variables will include number of participants with evaluable information and percentage based on number of participants with evaluable information.

The choice of statistical test will be guided by the objective and the type of measurement: Pearson's chisquare test for comparing distributions of categorical measures (Fisher's exact test where cell counts do not support Pearson), 2-sample t-test for comparing two means of interval scale measures, analysis of variance for comparing >2 means of interval scale measurements or two means with a covariate, Cox proportional hazard regression for comparing distributions of time to event, logistic regression for comparing rates of categorical measures, and Poisson regression for comparing rates of events.

#### 8.2. Demographics and Other Baseline Characteristics

Location, age group, sex, self-reported race and ethnicity, occupation, preexisting medical conditions, SARS-CoV-2 vaccine history during prior seasons (as feasible), and frequency of mask-use while in close proximity of others during the SARS-CoV-2 circulation period will be summarized overall and by vaccine group. All demographics and baseline characteristics will use the mITT population.

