5.1 Overview of Study Design

Approximately 1,500 adults 18 years and older from Salt Lake City, UT and surrounding areas (60-mile radius) will be enrolled in a randomized trial to be followed until Summer 2024. This trial will employ a stratified recruitment approach to ensure there is sufficient variability in sex and age within the cohort. For those that are in the intervention group, their randomization occurs at their vaccination appointment. Information on socio-demographics, employment information, occupational responsibilities, exposure to SARS-CoV-2 virus, history of SARS-CoV-2 infection, COVID-19 and flu vaccine history, health status and conditions, PPE use, pre-vaccination intention, and knowledge and attitudes about SARS-CoV-2 infection control practices will be collected by self-report through an enrollment survey. Information on previous COVID-19 vaccination history and concomitant medications will be collected at enrollment by study staff.

[figure not shown]
Following participant enrollment, active surveillance will be conducted weekly to identify acute illness symptoms via secure short message service (SMS) text messages. Participants will also be asked to proactively notify study staff if they develop symptoms during the week. To determine acute illness, participants will be asked if they developed subjective COVID-like illness (CLI) symptoms since the day of their last scheduled surveillance. CLI symptoms include fever, chills, malaise, fatigue, headache, cough, shortness of breath, sore throat, runny nose or nasal congestion, nausea or vomiting, diarrhea, muscle or body aches, and change in smell/taste. Each week, regardless of symptoms, participants will self-test with an at-home COVID-19 rapid antigen test (RAT) and upload a photo of the results to the database platform. When an acute illness and/or a positive COVID-19 test is identified, participants will self-test with an at-home COVID-19 antigen test on day 0, day 1, and test again on day 3. When illnesses are identified, participants will describe their symptoms, illness severity, duration, impact on functioning through resolution of their illness, and report any treatments/interventions and medical visits for SARS-CoV-2 infection.

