Study Duration: Study activities will commence following Institutional Review Board (IRB) approval. We aim to begin recruitment activities, i.e., identifying and screening potential participants, in November 2023. We anticipate initiating enrollment in November 2023 and start data collection immediately after enrollment. The vaccine campaign is estimated to begin in November 2023 and end in February 2023. All participants will start active surveillance immediately following their enrollment visit. Participants will complete all surveillance activities for a total of 24 weeks from the date of enrollment/vaccination. Surveillance activities are estimated to end Summer 2024. Close-out activities will begin in September 2024.

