5.5.4 Follow-up Surveys

Brief surveys will be administered over the course of the study for three purposes. First, surveys will allow participants to update information on their occupation and work responsibilities, health status, potential exposures to COVID-19 at work, home, and in the community, and their use of PPE in these settings. Second, surveys will allow participants to report if they were unable to report a qualifying illness and/or submit illness specimens for any reason, and to provide an estimate of when this missed illness event occurred so that their surveillance record can be updated accordingly. Third, surveys will assess participants KAP regarding COVID-19 vaccines, intention to be vaccinated, and then after vaccination, to recall their overall health status on the days following vaccination.

- Post-Vaccination Survey (Appendix W. Post-Vaccination Survey), for participants who choose to receive a COVID-19 2023-2024 updated vaccine, will be administered 24 hours ±1 day, 48 hours ±1 day, and 6 days ±1 day after receiving the vaccine in order to monitor events for 168 hours following vaccination.
- Follow-up Survey 1 (Appendix O. Mid-Study Survey) will allow participants to report any adverse
 events following immunization (AEFI), and update chronic medical conditions, KAP responses,
 occupational, exposures, PPE use, and employer-mandated COVID-19 vaccination requirements.
 This survey will also give participants an opportunity to report their influenza vaccination status
 for the season. Participants also can report any illnesses missed during surveillance. All

- participants will be asked supplemental questions to collect information about receipt of COVID-19 vaccines outside of the study during the study period.
- Follow-up Survey 2 (Appendix O. End-of-Study Survey) will provide a final opportunity to allow participants to report any AEFI, and update chronic medical conditions, KAP responses, occupational, exposures, PPE use, and employer-mandated COVID-19 vaccination requirements. This survey will also give participants an opportunity to report their influenza vaccination status for the season. Participants also can report any illnesses missed during surveillance. All participants will be asked supplemental questions to collect information about receipt of COVID-19 vaccines outside of the study during the study period.

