#### 6. ANALYSIS POPULATIONS

#### **6.1 Modified Intent-to-Treat Population**

All participants who are randomized, received a study vaccine, and participated in study surveillance by responding to at least one surveillance contact during the SARS-CoV-2 circulation period (active surveillance) will be included in the modified intent-to-treat (mITT) population for the primary objectives. The mITT population will be the primary population for efficacy analyses and participants are analyzed according to their randomized treatment. For participants who were identified as not receiving a booster

(comparison group) they will be analyzed in that group under the mITT population, even if they subsequently do get a vaccine during the study period.

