# 7. GENERAL ISSUES FOR STATISTICAL ANALYSIS

# 7.1 Adjustment for Covariates

Cox proportional hazard models will have vaccine group as the main effect. For the primary objectives age, prior COVID-19 vaccination in the preceding 3 years and week will be adjusted for (time-varying covariate). Prior COVID-19 vaccination will be categorized (1 prior vaccine (2 course vaccination), 2 prior vaccines (initial vaccination and 1 booster), 3 prior vaccines and  $\geq$ 4 prior vaccines), if there are less than 30 people in a category, then we will collapse down (e.g.  $\geq$ 3 instead of 3 and  $\geq$ 4) until we have stable estimates.

Other baseline characteristics will be included as covariates if there are significant imbalances between vaccine groups and kept in the model if they adjust the hazard ratio by  $\geq 5\%$ . If there is evidence that the proportional hazard assumption is not met, weekly SARS-CoV-2 circulation will be added as a covariate or will be investigated for stratifying the baseline hazard. Covariates will not be used in subgroup models, where they are the event of interest. Season will not be included in models of SARS-CoV-2 type and subtype if they only occur in one season. If an analysis has <10 events, an unadjusted model only will be calculated.

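### Mask use during follow-up is listed as a baseline characteristic, so the covariate rule makes it eligible for the primary VE model, where adjusting for it could bias VE in either direction

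*SAP*

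**What the plan says.** **The variable.** SAP 8.2 is headed as covering demographics and other baseline characteristics. Its list ends with mask use: "frequency of mask-use while in close proximity of others during the SARS-CoV-2 circulation period will be summarized overall and by vaccine group". The next sentence treats the whole list as baseline: "All demographics and baseline characteristics will use the mITT population". The protocol's descriptive-analysis paragraph in section 6.2 repeats both sentences.

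**The period.** SAP 6.1 makes mITT membership depend on "responding to at least one surveillance contact during the SARS-CoV-2 circulation period (active surveillance"), and Protocol 6.2 uses the same gloss. Protocol 5.2 dates the start: "All participants will start active surveillance immediately following their enrollment visit". For vaccinated participants, that visit is when the vaccine is given.

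**The covariate rule.** SAP 7.1 states: "Other baseline characteristics will be included as covariates if there are significant imbalances between vaccine groups". Such a covariate is "kept in the model if they adjust the hazard ratio by" at least 5%. SAP 8.3.1 and Protocol 6.1.2 repeat the rule for both primary objectives but print the threshold as 5 without a unit. None of the three limits candidates to pre-vaccination values or excludes mask use.

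**The data sources.** Protocol 5.1 places a pre-vaccination measure at enrollment: "PPE use, pre-vaccination intention, and knowledge and attitudes about SARS-CoV-2 infection control practices will be collected by self-report through an enrollment survey". Protocol 5.5.1.1 requires that survey before the visit can be scheduled. Protocol 5.5.4 adds later measures: "surveys will allow participants to update information on their occupation and work responsibilities, health status, potential exposures to COVID-19". That paragraph goes on to cover PPE use, and the Mid-Study and End-of-Study Surveys both update it. No section says which survey supplies mask-use frequency.

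**The concern.** A covariate in a model for the total effect of vaccination should be fixed before vaccination. Mask use over the surveillance period is not. Participants choose vaccination or refusal and know which they chose (Protocol 5.5.3, Blinding), so vaccination can change how much they mask. Time at risk ends at illness onset (SAP 7.5), so a mask report given after an infection can reflect that infection. The variable can therefore be a consequence of exposure, of outcome, or of both.

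The screening rule does not protect against this. Vaccinees and decliners may well differ in masking, which would meet the imbalance condition. The retention condition then keeps a covariate because it moves the hazard ratio, and reverse causation is one way to move it. At stake is the VE estimate for the first primary objective, on which the sample size is based.

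**Working it through.** **1. Is the variable eligible?** The SAP labels it baseline (8.2), the period is active surveillance (6.1), and surveillance follows the vaccination visit (Protocol 5.2). The rule admits imbalanced baseline characteristics without a date limit (SAP 7.1, 8.3.1). It is eligible on the text. The enrollment survey precedes the visit and so cannot cover the named period. The follow-up surveys that update PPE use are the likely source, by inference.

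**2. The plan's own figures.** Protocol 6.1.1 gives 60 per 100,000 person-days in the unvaccinated and 48 in the vaccinated, over 24 weeks (168 days), with 300 and 1200 enrolled. Its 10.08% is 0.0006 × 168, and its 0.10625 is −ln(1 − 0.1008); both reproduce. (SAP 4.1 prints 80 and 68; the protocol's rates are used here.) Treating the rates as hazards:

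- vaccinated risk = 1 − exp(−0.00048 × 168) = 7.75%, or 93.0 cases of 1200
- decliner risk = 1 − exp(−0.0006 × 168) = 9.59%, or 28.8 cases of 300
- crude OR = (0.0775/0.9225) / (0.0959/0.9041) = 0.792

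**3. Would the imbalance screen fire?** The documents give no masking rates, so these are assumptions. For 40% versus 20%, the pooled proportion is 0.36, SE = √(0.36 × 0.64 × (1/1200 + 1/300)) = 0.031, and z = 6.5. For 30% versus 20%, z = 0.10/0.029 = 3.5. A self-selected difference of that size would be flagged.

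**4. Effect of adjusting.** Assume masking has no effect on infection, so there is no confounding to remove. Uninfected people mask at the stated rates, and infected people report d points more or fewer. The Mantel-Haenszel OR over the two mask strata is Σ(ad/N) / Σ(bc/N), where a and b are infected and uninfected vaccinees, and c and d are infected and uninfected decliners.

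Example with 40% versus 20% and infected people reporting 20 points more:

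- masked: a = 55.8, b = 442.8, c = 11.5, d = 54.2, N = 564.3
- unmasked: a = 37.2, b = 664.2, c = 17.3, d = 217.0, N = 935.7
- OR = (5.36 + 8.62) / (9.03 + 12.25) = 0.657

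| Change in masking reported by infected people | 40% vs 20% | 30% vs 20% | 30% vs 30% |
|---|---|---|---|
| 20 points less | 0.945 | 0.878 | 0.792 |
| 10 points less | 0.865 | 0.833 | 0.792 |
| none | 0.792 | 0.792 | 0.792 |
| 10 points more | 0.723 | 0.753 | 0.792 |
| 20 points more | 0.657 | 0.716 | 0.792 |
| 30 points more | 0.593 | 0.679 | 0.792 |

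In the first column, 1 − OR runs from 5.5% to 40.7%, against 20.8% crude. Every shift there exceeds 5%, so the covariate would be kept. In the second column, 10 points more gives 0.753/0.792, a 4.9% change, just under the threshold.

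**5. Allowing masking to protect.** A constant-hazard model with an assumed masking HR of 0.7, true VE 50% and 40% versus 20% masking at enrollment gives:

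- unadjusted: 53.2%
- adjusted for enrollment masking: 50.0%
- adjusted for circulation-period masking: 58.9% or 66.0% if 30% or 60% of infected non-maskers start masking; 46.5% or 42.8% if 30% or 60% of infected maskers stop

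With true VE of 0, circulation-period adjustment gives −14.0% to +31.5%, while enrollment adjustment gives 0.0%.

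The path from vaccination to masking matters too. Take equal enrollment masking (30% in both groups) and let 30% of vaccinated maskers stop after vaccination. The total effect is then 48.5%, and circulation-period adjustment gives 43.5% or 36.1% if 30% or 60% of infected non-maskers start masking. With equal masking and no effect of vaccination on it, the shift is about 1 point or less.

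**6. The rVE comparison.** With blinded 1:1 randomisation and 30% masking in both arms, the shift is under 0.5 points at HR 0.9 to 1.0. It is at most about 2.4 points at HR 1.5 (−50.0% to −47.6%).

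**The case against.** SAP 8.2 commits only to a summary, and the protocol's matching paragraph sits under a descriptive heading. A careful analyst could read baseline in its ordinary sense and use enrollment values only. The source survey is not named, and Protocol 5.5.4 speaks of PPE use, not mask frequency. In calendar terms, some enrollment answers could fall within the season of virus circulation. Mask use would also have to pass both the imbalance screen and the change-in-HR rule. Finally, circulation-period masking may partly stand in for habitual masking, which is a plausible confounder, so adjusting for it could remove some bias as well as add some.

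Much of this stands as a limit on the claim. A reader might infer that the plan commits to adjusting for post-vaccination mask use, or that VE will be inflated. The documents support neither. The variable is eligible, not specified, and the direction depends on behaviour for which they give no data.

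The ordinary-meaning argument does not dispose of the point. The SAP itself calls this measure baseline, its own gloss places the period in active surveillance, and no sentence limits candidates by date. An analyst following the written rule could enter it.

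**Conclusion.** The point holds as a gap in the covariate rule. A measure taken after vaccination, and probably in part after infection, is labelled baseline and is therefore eligible for the primary Cox models. The timing relative to infection is inferred from the window and the survey schedule; the plan does not state it.

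The consequence is confined in practice to the first primary objective, the open comparison of vaccinated participants with decliners. On the assumed 40% versus 20% masking, the OR of 0.79 could become anything from 0.59 to 0.95. With equal masking in this illustration it does not move. These figures show what the rule permits; they are not forecasts. They rest on assumed masking rates and assumed changes after infection, and the main table also sets the effect of masking on infection to zero. The randomised rVE comparison is nearly unaffected. This should be corrected before unblinding, but it is not a demonstrated bias in the primary result.

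**What to change.** 1. In SAP 7.1 and 8.3.1 and Protocol 6.1.2, state that only characteristics measured at or before Day 0 may enter the primary models as additional baseline covariates. Week, already specified as time-varying, is unaffected.
2. In SAP 8.2 and the protocol's descriptive paragraph, name the Enrollment Survey PPE or mask item as the baseline measure and the candidate covariate. Protocol 5.1 says PPE use is collected there, but the itemised content in 5.5.1.1 lists neither PPE nor masks, so confirm that the instrument covers masks.
3. Report circulation-period mask use separately, by group, as a post-vaccination behaviour, and name its source survey.

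Removing mask use altogether would be the wrong remedy, because pre-vaccination masking may confound the comparison (53.2% unadjusted against a true 50% in the illustration). If the enrollment survey covers masks, the cost is wording only. The downside is that the enrollment item may be a coarser measure of masking. If it does not cover masks, the SAP should say that no pre-vaccination mask measure is available for adjustment.

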#### 8.3. Efficacy Analysis

# **8.3.1** Primary Objective Analysis

The primary analysis for VE will be a superiority test comparing vaccine efficacy (VE) between participants who receive either the NVX 2023-2024 updated vaccine (Arm 1) or Pfizer mRNA 2023-2024 updated vaccine (Arm 2) with the participants who are recommended to be vaccinated based on CDC, state or organizational guidelines but decline the 2023-2024 updated vaccine. Cox proportional hazards models will use the Andersen and Gill counting method with participants able to contribute time at risk for each day of follow-up. Vaccine efficacy is defined as 100% × (1–HR) calculated using the Cox proportional hazards regression with vaccine group as a main effect, adjusting for age group.

$$h(t) = h_0(t) \exp(\beta V + b_i Z_i)$$

where t is the time at risk,  $\beta$  is the effect of vaccine group of interest (different for VE and rVE objectives) and  $b_i$  is the effect of covariates indicated by  $Z_i$ . The HR for VE or rVE is then defined as  $exp(\beta)$ .

For the VE objective, Cox proportional hazard models will have randomized vaccine group versus the non-randomized arm as the main effect. For both primary objectives age, prior COVID-19 vaccination in the past 4 years and week will be adjusted for (time-varying covariate). Prior COVID-19 vaccination will be categorized (1 prior vaccine (2 course vaccination), 2 prior vaccines (initial vaccination and 1 booster), 3 prior vaccines and  $\geq$ 4 prior vaccines), if there are less than 30 people in a category, then we will collapse down (e.g.  $\geq$ 3 instead of 3 and  $\geq$ 4) until we have stable estimates. Other baseline characteristics will be included as covariates if there are significant imbalances between vaccine groups and kept in the model if they adjust the hazard ratio by  $\geq$ 5. If an analysis has <10 events, an unadjusted model only will be calculated.

If models for a single month do not meet the proportional hazard assumption, the Andersen and Gill counting method will be used to allow for weekly circulation as a covariate. If a model still does not meet the assumption the proportional hazards assumption after the inclusion of weekly circulation as a covariate, the Prentice, Williams, and Peterson total time model will be used with season as a strata and circulation as a covariate, allowing for circulation to vary. Participants who do not experience a SARS-CoV-2 case prior to the discontinuation of the study will be right censored at their last response to weekly surveillance contacts.

The relative vaccine efficacy against SARS-CoV-2 illness for NVX boosted participants versus mRNA boosted participants will be calculated with the mITT population using time at risk with the following null and alternative hypotheses for the objective comparing NVX vs mRNA:

$$H_0$$
: rVE < -50 and  $H_a$ : rVE $\geq$  -50

Here rVE is estimated with the same analytic approach described for the VE, however the Cox proportional hazard models will have NVX arm versus the Pfizer arm as the main effect. The primary objective will be achieved if the lower limit of the one-sided 95% confidence interval of rVE estimate exceeds -50 between NVX and Pfizer mRNA vaccine groups, adjusting for potential confounders or differences in baseline groups.

